This project is part of a competitive revision that aims to accelerate COVID-19 testing in underserved populations. The overall aim is to accelerate COVID testing in 9 hotspot communities in MA, through 6 community health center (CHC)-community partnerships. These CHCs have 141,000 patients, and their communities have over 1.3M residents. The implementation of *accelerated testing efforts will be focused on CHC patients and community members who have significant social and medical vulnerabilities to COVID, including those living in congregate housing, people experiencing homelessness, those with substance use disorders, low wage essential workers, and those with limited English proficiency*. The partnership is well-integrated into the State's testing and contact tracing strategy and leverages those resources. We will support the CHC-community partnerships through a team of community health and infectious disease expertise with technical guidance on COVID testing. We have an established partnership with the Massachusetts League of Community Health Centers to support this community-engaged, equity-focused approach to implementation of COVID-19 testing strategies. This is a multi-project research center. The aim of the project proposed here is:

- 1. Create and implement a community-partnered infrastructure that will accelerate COVID-testing and contact tracing among underserved and vulnerable populations in nine “hotspot” communities as measured by change in testing rate and equity in testing (by race/ethnicity).** We will use a controlled interrupted time series design to evaluate the impact of enhanced outreach and capacity building on testing rates and contact tracing overall and on priority populations compared to a set of matched control clinics. The point-of-care COVID diagnostics will focus on the four MGH Health Center communities which fall in the aforementioned nine “hotspot” communities.
- 2. Determine the impact of key implementation process strategies, such as tailored communication and outreach, on testing among LEP and other priority populations.** We will add tailored strategies based on barriers faced by priority populations within partner communities to the outreach and capacity building strategies in Aim1 and measure the impact of the tailored strategies using a stepped wedge design.

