VI. BIOSTATISTICAL ANALYSIS

a. Specific data variables being collected for the study (e.g., data collection sheets).

As part of routine care in the testing process, CHCs will collect demographics (age, gender, race, ethnicity, sexual orientation, preferred language), symptoms (fever, cough, dyspnea, fatigue, sore throat, headache, myalgia, new loss of taste or smell, runny nose or nasal congestion, nausea, vomiting, diarrhea, rash), socioeconomic status (insurance, educational level, zip code), job status (employed/unemployed) and job characteristics (essential worker/non-essential worker), household characteristics (number of people living in the home,), social needs (housing instability, food insecurity), existing primary care site, ease of accessing testing, disability status, personal impacts of COVID, COVID vaccine acceptance, COVID vaccine status, vaccine type, and vaccine date (MGH dates masked before sharing). In Chelsea, Massachusetts where COVID-19 wastewater surveillance data is being used to direct mobiles testing efforts, individual addresses will be collected for the purpose of determining which wastewater sampling site (i.e.

“sewershed” area) they fall into. Individual addresses will be analyzed at MGH and this data will not be shared with the data coordinating center at Dana Farber. Medical history and comorbidities that alter COVID-19 risk (chronic kidney disease, chronic lung disease, on immunocompromising medications, obesity [BMI>30], heart disease, CD4 count < 200, sickle cell disease, type 2 diabetes, smoking status, immunocompromised condition, autoimmune disease, hypertension, cancer, abdominal pain) will be collected in the CHC data reporting systems for those who are CHC patients.

An additional analysis will be conducted of patients that were tested for COVID-19 at MGH Chelsea between November 2020 and March 2021 to understand how COVID-related risk factors (obesity and smoking status) may vary by race, gender, ethnicity and language. This analysis will utilize the same dataset listed above; no other data variables will be included.

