The following data elements will be collected at each CHC as part of routine care to supplement EHR data. At MGH CHCs this is collected using an online REDCap survey or paper version of the REDCap survey. The paper REDCap survey will be entered into REDCap by a member of the research team. Federally qualified CHCs will use data collection methods (paper survey, online survey, phone) consistent with their usual care workflows for patient data collection aiming to improve clinical processes and understand the reach of services offered:

- Do you speak a language other than English at home? What languages?
- What is the highest level of education you have achieved outside or in the US?
- Including you, how many people live in your household?
- Are you currently living in transitional housing, staying in a shelter, or experiencing homelessness?

- Have you, or has anyone in your household experienced a loss of employment income since the start of the COVID-19 pandemic (March 2020)?
- Are you considered an essential worker? An essential worker is someone who was required to go to work even when stay at home orders were in place.
- Do you have a disability that interferes with your ability to carry out daily activities? Examples of daily activities include walking, climbing stairs, shopping, balancing a checkbook, bathing or dressing.
- It is easy to get tested for COVID-19.
- How likely are you to get an approved COVID-19 vaccine when it becomes available.
- Why would you get a COVID-19 vaccine?
- Why would you NOT get a COVID-19 vaccine?

Specific data to be collected through the individualized implementation support meetings with CHC staff will include details of their expanded testing strategy, populations reached, successes, challenges, how they are addressing equity and ways the implementation research team can support their site.

The data collected for the MGH sub study will not be shared with data coordinating center at Dana Farber.

b. Study endpoints

The primary outcome will be total number of daily and weekly tests. Secondary outcomes will include time to return of results, number of positive tests, completion of contact tracing, number of hospitalizations, intensive care admissions, and deaths. We will examine outcomes related to key socio-demographic and clinical covariates.

VII. RISKS AND DISCOMFORTS (Stratify by common and uncommon)

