### *Interrupted Time Series*

We characterized the implementation timeline of the planned testing acceleration strategies including funding notification and the start date of implementation activities. For the implementation activities start date, we considered that the CHCs made decisions about staffing and activities at the point of funding notification with the understanding that significant resources for RADx-MA were coming. They were then asked to start implementation activities with practice facilitation support on December 1, 2020. We considered both timepoints in the analyses and interpretation. We aggregated daily testing across the six CHCs and compared post-implementation testing trend with pre-implementation testing trend. Tests per week were modeled using segmented generalized linear model with number of weeks since start of pre-implementation period, indicator for pre- vs. post-implementation date, number of weeks post-implementation, weekly number of new state-wide covid cases, interactions of new covid cases with post-implementation week, and season of year to control for seasonality. Weekly number of new covid cases was included on the log-scale, centered at the number of cases on the implementation week, and divided by 10 to aid in interpretation. The coefficients of interest were for (a) the post-implementation week and (b) the interaction of post-implementation covid cases and post-implementation week. The former estimates the change in covid testing trend post-implementation relative to pre-implementation holding new covid cases at the implementation week level. The latter estimates the percentage change in covid testing trend post-implementation relative to pre-implementation for a 10% increase in new covid cases. We used heteroscedastic and autocorrelation consistent standard errors implemented using the Sandwich package in R. We consider  $\alpha=0.05$  as the threshold for statistical significance.

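### Aim 1 is to be judged partly on equity in testing by race/ethnicity, but no equity endpoint is listed and the primary model, a single pooled total, cannot show whether equity improved or worsened

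*Protocol*

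**What the plan says.** Protocol section II (Specific Aims) states that the first aim is to be assessed "as measured by change in testing rate and equity in testing (by race/ethnicity"). It adds that the time-series design will evaluate the effect "on testing rates and contact tracing overall and on priority populations compared to a set of matched control clinics".

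Protocol VI.b sets the endpoints. "The primary outcome will be total number of daily and weekly tests". Then: "Secondary outcomes will include time to return of results, number of positive tests, completion of contact tracing, number of hospitalizations, intensive care admissions, and deaths". The only sentence there that touches on population groups is "We will examine outcomes related to key socio-demographic and clinical covariates".

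The SAP (Interrupted Time Series) describes the primary analysis: "We aggregated daily testing across the six CHCs and compared post-implementation testing trend with pre-implementation testing trend". The model terms are calendar week, a pre/post indicator, post-implementation week, state-wide new cases, the interaction of cases with post-implementation week, and season. "The coefficients of interest were for (a) the post-implementation week and (b") the cases-by-post-week interaction. The power section covers the number of tests only.

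The data for an equity analysis are planned: Protocol VI.a lists "demographics (age, gender, race, ethnicity, sexual orientation, preferred language") among the items that the centers collect.

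**The concern.** The aim names two yardsticks and the endpoint list carries only one of them forward. The general sentence on covariates names no groups, contrast, metric, model or place in the endpoint hierarchy, so it does not say what result would count as better or worse equity. The primary model has no term through which race/ethnicity could enter.

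What is at stake is the reading of Aim 1. A rise in total tests that came mainly from groups already well served would give a positive coefficient (a) and could be reported as meeting the aim, while the second yardstick moved the wrong way unseen. For a project whose stated approach is equity-focused, that is the result a reader would most want to rule out.

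**Working it through.** **1. The plan's own figure.** The SAP states more than 90% power for a 3.5% weekly acceleration. Its inputs are 212 tests per day, a flat trend and 518 days split equally (259 + 259 days, or 37 + 37 weeks). For a segmented log-linear count model with day-of-week terms and two-sided α = 0.05 (sidedness is assumed), power = Φ(log(1.035)/SE − 1.96), with log(1.035) = 0.0344. The overdispersion φ is not stated, so it was varied:

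| φ | SE of post-week slope | Power |
|---|---|---|
| 1 | 0.0005 | about 100% |
| 100 | 0.0050 | about 100% |
| 200 | 0.0070 | 99.8% |
| 400 | 0.0099 | 93% |
| about 459 | – | 90% |

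The stated power is consistent with its inputs and is not in dispute. It concerns the pooled total and carries no information on equity.

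**2. Aim against endpoints.**

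| Aim 1 element (Protocol II) | Endpoint in VI.b | Term in the SAP model |
|---|---|---|
| Change in testing | Number of daily and weekly tests | Coefficients (a) and (b) |
| Equity by race/ethnicity | None named | None |

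**3. What a pooled slope can hide.** Take two groups with equal testing at the start and growth rates g1 and g2 on the log scale; both are assumptions. The pooled slope is the regression slope of log(exp(g1·w) + exp(g2·w)) on w = 0 to 37. The group ratio at week 37 is exp((g2 − g1) × 37).

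- g1 = 0.02, g2 = 0: pooled log-slope 0.0118, about 1.2% per week; ratio exp(−0.74) = 0.48.
- g1 = 0.015, g2 = 0.005: pooled log-slope 0.0105, about 1.05% per week; ratio exp(−0.37) = 0.69.

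**4. The same at the SAP's effect size.** Let total tests grow 3.5% per week over 37 post-implementation weeks (36 steps from first to last): 1.035^36 = 3.45 times baseline. Suppose group B supplies half of baseline tests and stays flat at 0.50. Group A must then reach 3.45 − 0.50 = 2.95, and the B:A ratio relative to baseline is 0.50/2.95 = 0.17. With B at 30% or 70% of baseline tests the ratio is 0.22 or 0.11. If B grows 3.5% per week like the total, the ratio is 1.00.

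In 300 simulated weekly series per scenario (74 weeks, pre-implementation mean 212 × 7 = 1,484, φ of 1 and 20), the total-count model was positive in 100% of runs whether the ratio was 1.00 or 0.17. That is expected, because the total has the same mean in every scenario. Adding group terms, the group × post-week coefficient detected the divergence in 100% of runs and rejected in about 4% to 8% when growth was equal.

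**5. Does a patient-count denominator matter?** Write the group model as log μ = log N_g + α_g + β_g·week + γ_g·post + δ_g·post-week + covariates. A constant N_g is absorbed by α_g. The contrast δ_B − δ_A is the same with or without it.

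**The case against.** The strongest reply is that a primary model need not answer every part of an aim, and that equity analysis is promised: the protocol commits to looking at priority populations and at socio-demographic covariates, and IX.c has an ethics unit attend to equity when monitoring outcomes. That stands as far as it goes. A reader might infer that the plan considers nothing but the total count, and the documents do not support this: VI.b lists six secondary outcomes, including contact tracing, which Aim 1 also names. What remains is that none of these provisions defines an equity endpoint, and oversight by an ethics unit is not one.

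Three further inferences should also be resisted.

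- *The SAP contains no equity analysis anywhere.* One part of the SAP, before the power section, was not available, and the power section refers to an overall primary outcome, which leaves room for others. The point rests on the endpoint list and the time-series section, both of which can be read.
- *The testing rate in Aim 1 has no counterpart.* Tests per week is a rate per unit time. A population denominator is one reading of the aim, not the only one.
- *Race and ethnicity are available for every test.* Protocol IX.b lists demographics as a minimum for tested non-patients, but a field that is collected is not a complete field. Section I.a cites missing race/ethnicity at health centers only as under 20%.

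It is also fair to say that the group trends above are invented and that outreach is directed at vulnerable groups, so divergence against them is not the expected direction. A pooled slope of 1.2% per week is about a third of the 3.5% the study was powered for, and no test was run on that example. The calculation at 3.5% per week does not have this weakness.

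**Conclusion.** The point holds in limited form. Aim 1 names equity by race/ethnicity as a measure, the protocol's endpoint list does not include it, and the primary model as written cannot inform it. The structural conclusion, that one pooled slope is compatible with stable, narrowing or widening group differences, needs no numerical assumption. The sizes do: ratios of 0.48 and 0.69 at week 37, or 0.11 to 0.22 at the SAP's own effect size with one group flat, depend on assumed shares and trends and are not predictions.

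A reader might go on to infer that inequity did widen, or that the primary result is invalid. Neither follows. The documents give no group-level data, and the total-count analysis remains a reasonable answer to the question it asks. This is a worthwhile and inexpensive improvement to the plan, not a fault in the primary test.

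**What to change.** - Build weekly test counts by race/ethnicity group, with an explicit 'unknown' stratum.
- Fit the same segmented model with group × week, group × post and group × post-week terms. The group × week term is needed so that divergence already under way before implementation is not credited to it. State whether the case terms are shared or group-specific, and compute standard errors that allow for groups sharing the same weeks.
- In VI.b, name the group difference in post-week slope, with its interval, as a secondary equity endpoint. State the reference group and which direction counts as improvement, since faster growth in a group that was under-tested at baseline would narrow the gap. Report it beside coefficient (a).
- Label it post hoc if it is added after the data were seen. The SAP is written in the past tense and its Study Design section records a choice made after looking at the daily series, so this probably applies.
- Do not require a patient-count offset. It leaves the slope contrast unchanged, and the tested population includes community members who are not patients (Protocol III.a, IX.b). If a per-person rate is wanted, restrict it to health center patients.

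The cost is one endpoint line and more analysis on data already planned for collection. Group slopes will be less precise than the pooled one. If the share with missing race changes over time, group slopes can be biased, and a separate stratum displays that problem without removing it; the share unknown should therefore be shown week by week.

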### ***Statistical power and sample size***

For the overall primary outcome of number of COVID-19 tests, we used an interrupted time series design, comparing the aggregated number of tests across the 6 RADx-MA before and after implementation. We conducted a simulation study to estimate power to detect a 3.5% acceleration in weekly testing at an  $\alpha = 0.05$  significance threshold. Population parameters were determined based on a preliminary analysis of a testing time series from 4 CHCs with available testing data between May 1 and July 11, 2000 (when testing was more widely available in Massachusetts). We observed an average of 212 tests per day, a flat time-trend, and no significant autocorrelation after adjusting for seasonality related to the day of the week. Further, we assumed 518 days in the time series with an equal number of days pre- to post-implementation. Based on these assumptions we estimated greater than 90% power to detect 3.5% weekly acceleration in testing.

### ***Study Design***

This study uses an interrupted time series analysis of COVID-19 testing data aggregated from six CHCs. Our original analysis planned to analyze the time series of daily COVID-19 testing volume, but daily data were noisy with a non-linear pre-implementation period. Because estimates from interrupted time series data can be sensitive to the choice of curve function pre- and post-interruption we decided to aggregate the data to weekly testing (which was linear pre-implementation) and implement an interrupted time series analysis.

### ***Statistical analysis***

Summary statistics were generated from the analytic dataset comprised of EHR-derived data, survey data, transformed facilitation data and publicly available contextual data to characterize the study sample.

### *Interrupted Time Series*

We characterized the implementation timeline of the planned testing acceleration strategies including funding notification and the start date of implementation activities. For the implementation activities start date, we considered that the CHCs made decisions about staffing and activities at the point of funding notification with the understanding that significant resources for RADx-MA were coming. They were then asked to start implementation activities with practice facilitation support on December 1, 2020. We considered both timepoints in the analyses and interpretation. We aggregated daily testing across the six CHCs and compared post-implementation testing trend with pre-implementation testing trend. Tests per week were modeled using segmented generalized linear model with number of weeks since start of pre-implementation period, indicator for pre- vs. post-implementation date, number of weeks post-implementation, weekly number of new state-wide covid cases, interactions of new covid cases with post-implementation week, and season of year to control for seasonality. Weekly number of new covid cases was included on the log-scale, centered at the number of cases on the implementation week, and divided by 10 to aid in interpretation. The coefficients of interest were for (a) the post-implementation week and (b) the interaction of post-implementation covid cases and post-implementation week. The former estimates the change in covid testing trend post-implementation relative to pre-implementation holding new covid cases at the implementation week level. The latter estimates the percentage change in covid testing trend post-implementation relative to pre-implementation for a 10% increase in new covid cases. We used heteroscedastic and autocorrelation consistent standard errors implemented using the Sandwich package in R. We consider  $\alpha=0.05$  as the threshold for statistical significance.

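### The SAP's two-segment model has no place for the weeks between funding notification and December 1, 2020; an added fit should exclude them or model them separately.

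*SAP*

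**What the plan says.** The SAP's Interrupted Time Series section describes two events. At the first, "we considered that the CHCs made decisions about staffing and activities at the point of funding notification", because the centers expected substantial resources. The second follows: "They were then asked to start implementation activities with practice facilitation support on December 1, 2020". The SAP adds that both dates entered the analyses and their interpretation.

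Daily tests are summed over the six CHCs, modelled by week, and the SAP "compared post-implementation testing trend with pre-implementation testing trend". The listed terms that carry the intervention are one pre/post indicator, one counter of weeks since implementation, and an interaction of that counter with new cases. The two coefficients of interest are (a), on the counter, and (b), on the interaction. The listed terms include no phase-in segment, and the section mentions no excluded weeks.

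Two other statements bear on this. Protocol section III.a reports that no suitable control series was found. SAP Study Design says that the weekly series was linear before implementation and that estimates can be sensitive to the curve chosen on each side of the break.

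**The concern.** By the SAP's own description, the weeks from notification to December 1 are neither clean baseline nor facilitated implementation, yet a two-segment model must place them in one or the other. With the break at December 1 they close the pre-period; with the break at notification they open the post-period. In both positions they lie at the end of a segment, where points have the most leverage on its slope, and (a) is a difference of slopes.

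If testing rose early, a December 1 break reads part of the rise as background trend and lowers (a). A notification break mixes phase-in weeks into the post slope, which can move (a) either way. With no control series, nothing outside the model would expose the error. What is at stake is the size of the headline trend estimate and, where there is no true slope change, its sign.

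**Working it through.** **Inputs from the SAP (Statistical power and sample size).**
- Length: "we assumed 518 days in the time series with an equal number of days pre- to post-implementation". 518/7 = 74 weeks, 37 before and 37 after.
- Level: "We observed an average of 212 tests per day, a flat time-trend, and no significant autocorrelation". 212 × 7 = 1,484 tests per week, flat.
- Effect: 3.5% weekly acceleration, read as a log-slope change s = ln(1.035) = 0.0344 per week.
- Alpha 0.05, taken as two-sided.

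**Assumed, because the text does not give them.** Gap L from notification to December 1 of 4, 8 or 12 weeks; the size and shape of any early change; the weekly coefficient of variation (CV). Case and season terms are left out.

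**Step 1: the plan's own figure.** The SAP states: "we estimated greater than 90% power to detect 3.5% weekly acceleration in testing". For m weekly points, the log-slope variance is CV² × v(m), with v(m) = 12/[m(m² − 1)]. v(37) = 12/50,616 = 0.000237, so SE(a) = CV × √(2 × 0.000237) = 0.0218 × CV. Power = Φ(s/SE − 1.96).
- CV 0.30: SE = 0.0065, power 99.95%.
- CV 0.45: SE = 0.0098, power 94.0%.
- Power falls to 90% at a CV of about 0.49.

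The statement is reproduced as an inequality. The issue here is bias, not the stated power.

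**Step 2: the model.** log μ(t) = β0 + β1·t + β2·P(t) + β3·P(t)·(t − T), where T is the break, P(t) = 1 from T onward, and (a) = exp(β3) − 1. Interval weeks have P = 0 if T is December 1 and P = 1 if T is notification.

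**Step 3: bias.** I fitted this as a Poisson model to noise-free means, with December 1 after week 37 and notification L weeks earlier. Entries are (a) in % per week for L = 4 / 8 / 12.

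| Assumed truth | True (a) | December 1 break | Notification break | Interval excluded |
|---|---|---|---|---|
| 30% step at notification, slope change from December 1 | 3.50 | 3.03 / 2.70 / 2.50 | 3.42 / 3.26 / 3.07 | 3.50 |
| Slope change phases in over the interval, no level rise | 3.50 | 3.48 / 3.40 / 3.25 | 3.46 / 3.40 / 3.34 | 3.50 |
| As above, plus a 20% level rise over the interval | 3.50 | 3.36 / 3.13 / 2.85 | 3.56 / 3.55 / 3.52 | 3.50 |
| Ramp to +30% over the interval, then flat | 0.00 | −0.18 / −0.39 / −0.55 | +0.19 / +0.28 / +0.32 | 0.00 |
| No change before December 1, then 30% step and slope change | 3.50 | 3.50 / 3.50 / 3.50 | – | 3.50 |

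In the first two rows both breaks fall below the truth. In the third and fourth they lie on either side of it. In the last, the December 1 fit is right; conversely, if the whole effect starts at notification, that break is the correct one.

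**Step 4: cost of excluding the interval.** The pre-segment shrinks to 37 − L weeks, so the SE ratio is √{[v(37) + v(37 − L)]/[2·v(37)]}.

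| L | v(37 − L) | SE ratio | Power, CV 0.30 | Power, CV 0.45 |
|---|---|---|---|---|
| 0 | 0.000237 | 1.00 | 99.95% | 94.0% |
| 4 | 0.000334 | 1.10 | 99.8% | 89.2% |
| 8 | 0.000493 | 1.24 | 98.9% | 80.8% |
| 12 | 0.000769 | 1.46 | 95.1% | 67.4% |

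In this simplified model, an interval segment with its own free level and slope gives the same (a) and the same SE as exclusion.

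**The case against.** The best defence is that the SAP describes choices made at notification, not testing that rose then. Resources were still to come, and activities were requested only from December 1. If testing did not move in between, the December 1 fit misclassifies nothing. SAP Study Design also reports a linear pre-implementation series, and a 30% jump in its last weeks should have been visible. This stands as a limit: bias in the December 1 fit needs an early effect that the documents do not assert. It does not settle the matter, because the linearity statement is not tied to either date.

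The second defence is that using both dates is already a sensitivity check. That is partly right: the ramp and mixed scenarios are bracketed. The step scenario is not, nor is the one where only the slope phases in.

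Third, a reader might infer that the SAP ran two separate fits and kept the interval weeks in each. It does not say so. It says only that both dates were used, and part of the SAP is not in the text available. The coding of those weeks is inferred from the listed terms.

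Fourth, a reader might conclude that exclusion should be the primary analysis. The SE increases do not support that as a rule; it trades bias against variance.

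**Conclusion.** The point holds in a limited form. The SAP describes an interval that its listed terms cannot represent, and no control series offsets the gap. If testing changed during the interval, (a) is in general biased. Under the 30% step the shortfall from 3.50 is 0.47 to 1.00 percentage points per week with the December 1 break and 0.08 to 0.43 with the notification break. Under a gradual slope phase-in it is only 0.02 to 0.04 points at 4 weeks, and at most 0.25 at 12. These figures rest on assumed gaps and effect shapes, with no noise and no case or season adjustment.

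Two stronger readings are not supported. The negative values of (a) in the ramp scenario do not show a working programme reported as harmful to the trend: the true slope change there is zero, and the benefit is a level change, carried by the pre/post indicator. Nor can the documents show that bias occurred, since they give neither the gap length nor evidence of an early rise. The missing notification date is not counted as an omission.

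**What to change.** State in the SAP how the weeks from funding notification through November 30, 2020 are coded under each break and, if it is not given elsewhere, the notification date. Add a pre-specified fit that leaves those weeks out or gives them their own level and slope, with the pre-trend taken from weeks before notification and the post-trend from December 1. Report it beside the fits at the two existing dates. If the three disagree, do not base the conclusion on (a) from a single break. If the analysis has already been run, as the SAP's past tense suggests, label the new fit as an added sensitivity analysis.

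The cost is a few lines of SAP text and one data filter or extra segment. The price in precision is in Step 4 of the working; it is a reason to keep this fit as a sensitivity analysis, especially if the gap is long.
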